7 MEASUREMENT OF EFFECT

7.1 Safety/Tolerability

AE assessment will be performed for all subjects. The study will use the Common Terminology Criteria for Adverse Events (CTCAE) 5. Physical examination, vital signs, laboratory tests will be performed. Vitals will be taken 10-30 minutes before/after infusion OR at the closest time points possible if not possible in the 10-30 minute period.

7.2 Efficacy

Reduction in the progression to acute respiratory failure [Time Frame: 15 days]

Patients with a baseline $\text{PaO}_2/\text{FiO}_2 \geq 200$: progression of respiratory failure is defined by:

- severe gas transfer deficit ($\text{PaO}_2/\text{FiO}_2 < 200$)
- persistent respiratory distress while receiving oxygen (persistent marked dyspnea, use of accessory respiratory muscles, paradoxical respiratory movements)

The rate will be calculated as the proportion of patients who experienced at least one of the events above by day+15 from treatment start.

8 ADVERSE EVENTS

8.1 Experimental Therapy

For the most recent safety update, please refer to the current uproleselan [IB](#).

Contraindications:

- Hypersensitivity to uproleselan or related products
- Interaction with other medications
- Adverse Reactions

Please refer to [Section 6.2](#) for details; these will be reported during the study.

8.2 Definitions

8.2.1 Adverse Event Reporting Requirements

Purpose: Adverse event data collection and reporting, which are required as part of every clinical trial, are done to ensure the safety of patients enrolled in the studies as well as those who will enroll in future studies using similar agents.

Adverse Event Reporting:

The descriptions and grading scales used in the revised NCI Common Terminology Criteria for Adverse Events (CTCAE) version 5.0 will be utilized for AE reporting. The CTCAE v5.0 mapping document can be downloaded at the CTEP website:

(https://ctep.cancer.gov/protocoldevelopment/electronic_applications/docs/CTCAE_v5_Quick_Reference_5x7.pdf)

Reporting requirements may include the following considerations: 1) the characteristics of the adverse event including the grade (severity); 2) the relationship to the study therapy (attribution); and 3) the prior experience (expectedness) of the adverse event.

Adverse events (AE) refer to any untoward medical occurrence associated with the use of an intervention in humans, whether or not considered intervention-related (21 CFR 312.32 (a)). By way of example and without limitation, an AE can be any unfavorable and unintended sign (for example, an abnormal laboratory finding), symptom, or disease temporally associated with the use of the Study Drug.

Protocol-defined and serious AE will be collected for 28 days following the first study drug dose, or death, whichever comes first. In addition, patients with drug related AE will be monitored until symptom resolution, even if the symptoms extend beyond the 28-day period.

AEs may include:

- Exacerbation (i.e., an increase in the frequency or severity) of a pre-existing condition. Illness present before study entry should be recorded in the medical history section of the CRF and only be reported as an AE if there is an increase in frequency or severity of the condition during the study.
- Intercurrent illnesses with an onset after administration of study drug begins.

AEs DO NOT include:

- Any medical condition or laboratory abnormality with an onset date before initial study treatment is considered to be pre-existing in nature. Any known pre-existing conditions that are ongoing at time of study entry should be considered medical history.
- Medical or surgical procedures (the condition that leads to the procedure is the AE)
- Situations where an untoward medical occurrence has not taken place. For example:
 - Planned hospitalizations due to pre-existing conditions, which have not worsened.
 - Hospitalizations that occur for procedures not due to an AE.
 - Hospitalization for the diagnostic procedure where the hospital stay is less than 24 hours in duration or for normal management procedures (i.e. chemotherapy).

Laboratory findings DO NOT need to be reported as AEs in the following cases:

- Laboratory parameters already beyond the reference range at screening.
- Abnormal laboratory parameters caused by mechanical or physical influences on the blood sample (e.g., in vitro hemolysis) and flagged as such by the laboratory in the laboratory report.
- An abnormal laboratory value that cannot be confirmed after repeat analysis,

preferably in the same laboratory.

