5.2 Assessment for Toxicities

Any subject who receives treatment on this protocol will be evaluable for toxicity. Each subject will be assessed for the development of toxicity according to the Time and Events Table (Table 3). Toxicity will be assessed according to the CTCAE v. 5.

All drug administration will be performed by nurses in the inpatient unit. Routine vital sign measurement will be performed and all adverse events (AEs) will be recorded. Toxicities will be classified as AEs probable, possible, unlikely or unrelated to uproleselan.

5.2.1

Evaluating for progression to Acute Respiratory Failure

- Reduction in the progression to acute respiratory failure [Time Frame: 15 days].
- Patients with a baseline PaO₂/FiO₂ \geq 200: progression of respiratory failure is defined by:
 - a. severe gas transfer deficit (PaO₂/FiO₂ < 200).
 - b. persistent respiratory distress while receiving oxygen (persistent marked dyspnea, use of accessory respiratory muscles, paradoxical respiratory movements).
- The rate will be calculated as the proportion of patients who experienced at least one of the events above by day+15 from treatment start.
- Overall survival and all-cause mortality (day 15, day 28).
- Time to improvement in oxygenation for at least 48 hours. Improvement in oxygenation is defined as an increase in PaO₂/FiO₂ of 50 (or greater) compared to the nadir of PaO₂/FiO₂.
- Number of patients requiring mechanical ventilation, if not on mechanical ventilation at study entry.
- Change in the WHO COVID-19, “8-point ordinal scale” from study entry to day 28 (Table 1). To be assessed on day 3, day 8, day 15, day 28.
- Duration of hospitalization and duration of ICU care.
- Toxicity assessment (including incidence of grade 3-5 hemorrhagic events).
- Change in D-dimer [Time Frame: baseline, study day 3, day 8, day 15, and day 28]. Changes in plasma D-dimer level compared with baseline at enrollment.
- Decrease or Change in IL-6:IL-10 ratios.

- Free-Days- at day 28
Oxygen
Ventilator
Vasopressor
ICU
Hospitalization

Table 1: WHO Ordinal Scale Ordinal Score

Patient State	Descriptor	Score
Ambulatory	No limitation of activities	1
	Limitations of activities	2
Hospitalized (mild disease)	No oxygen therapy	3
	Oxygen by mask or nasal prongs	4
Hospitalized (severe disease)	Non-invasive ventilation or high-flow oxygen	5
	Intubation and mechanical ventilation	6
	Mechanical ventilation + additional organ support – pressors, RRT, ECMO	7
Dead	Death	8

Exploratory Endpoints

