6.2 Study Schedule of Events

Table 4: Events of the Study

	Baseline	Day 1	Day 2	Day 3	Day 4	Day 5	Day 6	Day 7	Day 8	Day 15	Day 28
Eligibility screen	X										
Informed Consent	X										
Medical history	X										
Physical Exam	X	X	X	X	X	X	X	X			
CBC	X ^a	X	X	X	X	X	X	X			
Chemistries	X ^a	X	X	X	X	X	X	X			
ABG	X ^a										
CXR	X ^b										
Biomarkers ^g	X	X	X	X	X	X	X	X		X	X
D-dimer ^g	X			X					X	X	X
Serum pregnancy test	X ^c										
Pulmonary indices ^d	X	X	X	X	X	X	X	X	X	X	X
Uproleselan		X	X	X	X	X	X	X			
Vital Signs ^e		X	X	X	X	X	X	X			
COVID scale	X			X					X	X	X
AE and follow-up ^f		X	X	X	X	X	X	X	X	X	X

Key: CBC-complete blood count; CXR-chest X ray; ABG-arterial blood gas; BP-blood pressure; HR-heart rate; RR-respiratory rate.

Notes:

- a. Laboratory tests performed within 48 hours prior to study enrollment do not need to be repeated at baseline. CBC should be performed daily (until cessation of study therapy) and should be viewed as standard medical care. Arterial blood gas (ABG) measurements, and chest radiographs should be performed per routine medical care. Venous blood gas may be used when ABG unavailable. Patients should continue to have laboratory tests performed (as indicated above) until cessation of study therapy.
- b. Chest X-Ray (CXR): The CXR does not need to be repeated at baseline, if a CXR was done on admission and revealed bilateral infiltrates.
- c. Pregnancy test: Perform in subjects of child-bearing potential, if not already performed this admission for clinical care reasons.
- d. Pulmonary indices will be recorded daily until cessation of drug therapy, and again at day 8, 15 and 28 (if a patient remains hospitalized at that time). Patients who are discharged prior to day 15 or 28 do not need to have pulmonary indices assessed on day 15 or 28.
- e. Vital signs: heart rate, respiratory rate, blood pressure prior to and upon completion of each infusion.
- f. Adverse Event Reporting and Follow-up: Patients will be assessed for adverse events daily during receipt of study therapy, and for 7 days following completion of study drug therapy, provided they remain hospitalized during this 7-day post-therapy period. In addition, patients will be contacted on day 15 and 28 (± 2 days), to assess their clinical status and any active adverse events at that time. This final assessment can be done virtually, by telephone or electronically (email) if the patient cannot be contacted by phone. No in-person visit is required.

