8.5 Routine Reporting

All other adverse events, such as those that are expected, or are unlikely or unrelated to the drugs administered, are to be reported to the IRB annually as part of regular data submission.

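### Section 8.2.1, Section 5.2 and Table 4 note f give different scopes and windows for the adverse events behind the primary safety endpoint

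*Combined protocol and SAP*

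**What the plan says.** Sections 3.1 and 12.1 name safety as the primary endpoint without an AE variable, grade threshold or window. Section 12.3 plans descriptive statistics and frequency counts and does not say which AEs are counted.

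The capture rules are in several places:

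- Section 8.2.1: "Protocol-defined and serious AE will be collected for 28 days following the first study drug dose, or death, whichever comes first". Just before this, the same section defines AEs broadly: "Adverse events (AE) refer to any untoward medical occurrence associated with the use of an intervention in humans, whether or not considered intervention-related".
- Section 5.2: "Routine vital sign measurement will be performed and all adverse events (AEs) will be recorded". No window is given.
- Section 7.1: "AE assessment will be performed for all subjects".
- Table 4 note f (Section 6.2): "Patients will be assessed for adverse events daily during receipt of study therapy, and for 7 days following completion of study drug therapy", on condition that the patient is still in hospital. Contacts at days 15 and 28 (±2 days) then serve "to assess their clinical status and any active adverse events at that time".
- Section 8.5: "All other adverse events, such as those that are expected, or are unlikely or unrelated to the drugs administered, are to be reported". The recipient is the IRB, once a year.

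The follow-up rules also differ. Section 8.2.1 says that "patients with drug related AE will be monitored until symptom resolution, even if the symptoms extend beyond the 28-day period". Section 5.5 follows treatment-emergent AEs until they resolve or stabilize. Section 8.3.2 follows any detected AE to resolution.

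**The concern.** The primary result is a count of AEs, so the capture rule largely determines it. Section 8.2.1 uses a term, protocol-defined, that appears nowhere else and has no list attached. Nothing ranks Section 8.2.1 above or below Section 5.2. One coordinator could log every AE to day 28. Another could log a self-chosen subset plus SAEs. Each could point to protocol text.

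The schedule adds a second gap. Even if all AEs are meant, note f does not ask about the whole 28 days. With 15 planned patients, one patient more or less with an event moves a rate by 1/15 = 6.7 percentage points, and events not collected at the time may not be recoverable later.

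**Working it through.** The plan states no figure on this point, so there is none to reproduce. The check compares passages, counts days and makes one illustrative calculation.

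**1. Can protocol-defined be resolved from the protocol?** No list carries that label. Two candidates exist: the major-bleeding definition in Section 13 and the grade 3-5 hemorrhagic events in Section 3.2. Neither is called a protocol-defined AE. The cross-references do not help. Section 8.1 sends the reader to Section 6.2 for details of adverse reactions, but 6.2 is the visit schedule. Section 5.2 cites the time-and-events table as Table 3, but Table 3 lists standard-of-care treatments and the schedule is Table 4.

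**2. Readings of Section 8.2.1.**

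- *Broad:* AEs that meet the definition just given, plus SAEs. This agrees with Section 5.2. However, Section 8.2.2 defines an SAE as an AE with certain outcomes, so naming serious events separately would be redundant.
- *Staged:* all AEs during inpatient dosing, then a narrower set to day 28. This also fits Section 5.2, whose sentence sits in the paragraph on drug administration. The narrower set is undefined, and no passage says where the switch occurs.
- *Narrow:* a restricted set plus SAEs throughout. This conflicts with Section 5.2.

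**3. Windows.** Count the first dose as day 1 and the contacts at their nominal days.

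- Section 8.2.1: days 1 to 28.
- Note f, patient who stays in hospital: daily on days 1 to 7 plus 7 days, so days 1 to 14, then days 15 and 28. That is 14 + 2 = 16 of 28 days. Days 16 to 27 (28 − 16 = 12 days) have no scheduled AE assessment.
- Note f, patient discharged at the end of day 7: days 1 to 7, 15 and 28, so 7 + 2 = 9 of 28 days. The other 28 − 9 = 19 days have none. The Table 4 grid also marks day 8; counting it leaves 18.

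Days between contacts would not matter if the contacts looked back, but note f asks about AEs active at the contact. A non-serious AE that begins and ends in between therefore lies inside the Section 8.2.1 window (on the broad reading) and no scheduled question picks it up.

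**4. How far apart the readings could lie (illustration).** Inputs are from Section 1.3.

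- Subjects with a treatment-emergent AE: 49 of 86 volunteers and 100 of 103 patients. (49 + 100)/(86 + 103) = 149/189 = 78.8%.
- Subjects with an SAE: 36/189 = 19.0%.
- Subjects with an event but no SAE: at least 149 − 36 = 113, or 113/149 = 75.8%, if every subject with an SAE is among the 149.
- Volunteers alone: one SAE against 49 subjects with a treatment-emergent AE.

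**The case against.** A reader might infer that Section 8.2.1 reduces the primary endpoint to SAEs. The documents do not support that. The sentence contains no word such as *only*, and it covers protocol-defined AEs as well as serious ones. Much of the protocol presupposes non-serious capture:

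- Section 8.2.1 counts abnormal laboratory findings as possible AEs and lists when they need not be reported.
- Section 8.3.1 defines mild and moderate grades for events outside CTCAE.
- Section 8.3.2 follows any detected AE.
- Section 8.5 reports expected and unrelated events yearly.
- Section 14 provides for regular review of AE and laboratory data.

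A site that dropped non-serious AEs would also breach Section 5.2. Note f does not restrict the type of event; it differs in timing.

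The database figures have limits too. They come from healthy volunteers and from AML, multiple myeloma and DVT patients, and 101 of the 103 patients had chemotherapy alongside. In inpatients, a prolonged stay alone makes an event serious (Section 8.2.2), so the 76% share cannot be carried over to this trial.

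All of that stands against the stronger reading. It does not make the text consistent. The term remains undefined, the broad reading leaves words without a function, and the timing gap in note f is there on every reading. If the sponsor intends all AEs, as seems likely, the edit is easier.

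**Conclusion.** The scope and window of AE capture for the primary endpoint are inconsistent, and the protocol should be reconciled. Section 8.2.1 as worded leaves room to exclude an unspecified set of non-serious AEs from the 28-day collection. Following note f as written loses non-serious AEs that start and resolve between contacts after discharge.

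The size in this trial cannot be stated. SAE-only capture is the extreme case, and 149/189 against 36/189 illustrates its distance from all-AE capture in other populations. The day counts rest on nominal contact days and on note f being the operative schedule. The public text has a removed stretch between Sections 8.4 and 8.5. The contents list places Section 8.4.1, on SAE notification, there, so a list of protocol-defined AEs is unlikely in it, but this cannot be checked.

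This is a cheap improvement, severity should-fix: the analysis is descriptive and most passages already point to all-AE capture.

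**What to change.** 1. In Section 8.2.1, replace the collection sentence with: *All AEs of any grade, serious or not, with onset from first dose through Day 28 (or death, if earlier) are collected for every dosed subject.* Drop the term protocol-defined.
2. Align Section 5.2 and note f with it. The day 15 and day 28 contacts should ask about all AEs since the last assessment, with onset and resolution dates. The ±2 days allow the last contact at day 26 (28 − 2), so say whether collection ends at day 28 or at that contact.
3. Reconcile the AE follow-up wording in Sections 5.5, 8.2.1 and 8.3.2.
4. In Section 12.3, name the tabulations: any AE, grade 3 or higher, related, and serious, each as n/N of treated subjects.

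The cost is a few sentences across these sections, modest extra AE data entry, and slightly longer interviews at two contacts already scheduled, for 15 planned patients. Note f already allows these contacts without an in-person visit. Treatment does not change.

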COVID-19 ARDS appears to have worse outcomes than ARDS from other causes. The intensive care unit and hospital mortality from typical ARDS are 35.3% (95% CI, 33.3–37.2%) and 40.0% (95% CI, 38.1–42.1%), respectively.⁶ For COVID-19 ARDS, mortality ranged between 26% and 61.5% if ever admitted into a critical care setting, and in patients who received mechanical ventilation, the mortality can range between 65.7% to 94%. Risk factors for poor outcomes include older age; presence of comorbidities such as hypertension, cardiovascular disease and diabetes mellitus; lower lymphocyte counts; kidney injury; and raised D-dimer levels. Death from COVID-19 ARDS is due to respiratory failure (53%), respiratory failure combined with cardiac failure (33%), myocardial damage and circulatory failure (7%), or death from an unknown cause.⁷

Given the high mortality rate associated with COVID-19 ARDS, preventing progression of COVID-19 pneumonia in patients simply requiring supplemental oxygen to COVID-19 ARDS is a key priority and goal.

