4.2 Exclusion Criteria

1. In the opinion of at least one investigator, unlikely to survive for >48 hours from screening.
2. Severe chronic respiratory disease (e.g. COPD or other) requiring supplemental oxygen and/or having required mechanical ventilation pre-COVID-19 infection.
3. Concurrent enrollment in a COVID related interventional drug trial. Use of remdesivir, steroids, and convalescent plasma are permitted along with other standard of care therapies for COVID.³⁷
4. Currently on invasive mechanical ventilation.
5. Hypotension defined as systolic blood pressure < 90 mmHg on two sequential readings at least 4 hours apart.
6. Total Bilirubin ≥ 3 x upper limit of normal (ULN), Creatinine Clearance ≤ 30 mL/min/1.73m².
7. Pregnant or breastfeeding.
8. Known diagnosis of an acute thrombosis on admission.
9. Concurrent dual antithrombotic therapy (aspirin or P2Y₁₂ inhibitor plus anticoagulation to treat deep venous thrombosis or pulmonary embolism (single antiplatelet or anticoagulant agent at prophylactic dose is permitted).
10. Concomitant use of thrombolytic therapy.
11. Concomitant therapeutic systemic anticoagulant therapy (e.g. heparin, warfarin, direct thrombin inhibitors and direct factor Xa inhibitors). As per NIH Guidelines: Hospitalized adults with COVID-19 should receive VTE prophylaxis per the standard of care for other hospitalized adults (AIII). Anticoagulant or antiplatelet therapy should not be used to prevent arterial thrombosis outside of the usual standard of care for patients without COVID-19 (AIII); <https://www.covid19treatmentguidelines.nih.gov/therapeutic-management/>
12. History of recent major bleeding, defined in accordance with the criteria of the International Society on Thrombosis and Hemostasis (ISTH).
13. History of bleeding disorder thought to impose excessive bleeding risk as per investigator discretion
14. Hemodynamic instability, defined as inability to maintain mean arterial pressure.
15. Hypersensitivity to the active substance or to any of the excipients of uproleselan.
16. Any physical examination findings and/or history of any illness that, in the opinion of the investigator, might confound the results of the study or pose an additional risk to the patient by their participation in the study

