Life-threatening is defined as an adverse event or suspected adverse reaction in the view of either the investigator or sponsor, its occurrence places the patient or subject at immediate risk of death. It does not include an adverse event or suspected adverse reaction that, had it occurred in a more severe form, might have caused death.

Note that hospitalizations for the following reasons should not be reported as SAEs:

- Previously planned (prior to signing the informed consent form) surgeries should not be reported as SAEs unless the underlying medical condition has worsened during the course of the study.
- Preplanned hospitalizations or procedures for preexisting conditions that are already recorded in the subject's medical history at the time of signing informed consent form should not be considered SAEs.
- Hospitalization or prolongation of hospitalization without a precipitating clinical AE (for example, for the administration of study therapy or other protocol-required procedure)

should not be considered SAEs. However, if the preexisting condition worsened during the course of the study it should be reported as an SAE.

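### The laboratory exemption in Section 8.2.1 has no limit for worsening and is not reconciled with the exacerbation clause; secondarily, the Day 15 and Day 28 contacts do not ask about AEs that have already resolved

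*Combined protocol and SAP*

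**What the plan says.** **Laboratory findings.** Section 8.2.1 lists cases in which a laboratory finding need not be reported as an AE. The first is "Laboratory parameters already beyond the reference range at screening". Earlier in the section, under the heading for what AEs do not include, stands: "Any medical condition or laboratory abnormality with an onset date before initial study treatment is considered to be pre-existing in nature". The list of what AEs may include opens with: "Exacerbation (i.e., an increase in the frequency or severity) of a pre-existing condition".

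**Hospitalizations.** The corresponding exclusions do mention worsening. Section 8.2.1 exempts "Planned hospitalizations due to pre-existing conditions, which have not worsened", and Section 8.2.2 closes its list with "However, if the preexisting condition worsened during the course of the study it should be reported as an SAE".

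**Toxicity.** Section 5.2 makes every treated subject evaluable for toxicity, graded by CTCAE version 5, and adds: "Routine vital sign measurement will be performed and all adverse events (AEs) will be recorded".

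**Late contacts.** Under Table 4 note f, AEs are assessed daily during therapy and for 7 days afterwards, the latter only while the patient is in hospital. Contacts on Day 15 and Day 28 (±2 days) then cover clinical status and AEs active at that time. Section 8.2.1 collects protocol-defined and serious AEs for 28 days from first dose, but does not define the first of those terms.

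**Analysis.** Safety is the only primary endpoint (Section 3.1), with no count or threshold attached. Section 12.3 plans descriptive statistics and change from baseline for quantitative safety data, and frequency counts for qualitative safety data.

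**The concern.** Some patients will probably enter with laboratory values out of range. Exclusion 6 sets limits on two quantities only: "Total Bilirubin ≥ 3 x upper limit of normal (ULN), Creatinine Clearance ≤ 30 mL/min/1.73m²". A patient with bilirubin above normal but below three times the limit, or with reduced creatinine clearance above 30, is not excluded by it. Section 1.1 names "lower lymphocyte counts; kidney injury; and raised D-dimer levels" among the risk factors for poor outcome in this disease.

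If a value that was abnormal at screening deteriorates during the seven days of dosing, the literal bullet lets the site leave it unreported as an AE. It then carries no CTCAE grade as an AE and no attribution to drug. Renal values show why this matters: Section 9.1 says clearance depends on renal function and that more than 95% of the drug is excreted unchanged in urine.

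The late contacts raise a smaller form of the same problem. Where either provision is followed to the letter, it can only lower AE counts. Those counts are one of the two planned summaries of the primary endpoint, and AEs also feed the interim toxicity assessments (Section 12.1.2) and the monthly reviews (Section 14).

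**Working it through.** The plan gives no figure to reproduce here, so the check is mainly a comparison of texts.

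**1. Does any provision bring worsening laboratory values back in?**

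- *Section 8.2.1, bullet on onset before treatment.* It covers medical conditions and laboratory abnormalities together and calls both pre-existing. The exacerbation clause can therefore be read to reach both. The sentence that follows that clause, however, speaks of illness and of the condition, and does not name laboratory values.
- *Section 8.2.1, bullet on values out of range at screening.* It deals specifically with laboratory findings, comes later, and has no worsening limit or cross-reference. It is permissive: such findings need not be reported, but they may be.
- *Section 5.2.* All AEs are to be recorded, but Section 8.2.1 determines what has to be reported as one.

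Both readings are available, and nothing says which prevails. The hospitalization exclusions show that a worsening limit was written where one was wanted.

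**2. What would still show the change?** CBC and chemistries are drawn daily on Days 1 to 7 (Table 4), up to 15 × 7 = 105 panels of each. Change from baseline is summarised (Section 12.3), and all clinical data, laboratory data included, are reviewed regularly (Section 14). PT, aPTT and fibrinogen are required only at baseline (Section 6.1.1), so this backstop is weaker for them.

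**3. How would the literal rule act on counts?** Assume that a share p of the 15 patients truly worsens on some parameter, that a share q of those were out of range at screening, and that the exemption is used in every such case. The documents give neither p nor q.

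Expected patients reported = 15 × p × (1 − q)

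P(at least one reported) = 1 − [1 − p(1 − q)]^15

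For p = 0.20:

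| q | Expected patients reported | P(at least one reported) |
|---|---|---|
| 0 | 3.00 | 0.965 |
| 0.25 | 2.25 | 0.913 |
| 0.50 | 1.50 | 0.794 |
| 0.75 | 0.75 | 0.537 |

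The count falls by the fraction q. This shows the mechanism and is not an estimate of the undercount.

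**4. How long are the gaps between late assessments?** Daily assessment ends on Day 7 + 7 = Day 14 at the latest.

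- In hospital to Day 14, contacts on nominal days: Days 16 to 27 have no assessment, which is 27 − 16 + 1 = 12 days.
- Last daily assessment on Day 8: Days 9 to 14 are added, giving 6 + 12 = 18 days in two stretches.
- With the ±2-day windows, the contacts lie 26 − 17 = 9 to 30 − 13 = 17 days apart.

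Sections 5.5 and 8.3.2 require an AE to be followed once it is known. They do not ensure that it is found.

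**5. How relevant is that period to drug exposure?** Section 9.1 gives a half-life of 1.4 to 2.5 hours. One day after the last dose, 24/2.5 = 9.6 to 24/1.4 = 17.1 half-lives have passed. Most of the gap therefore follows drug clearance, with the caveat that clearance depends on renal function.

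**The case against.** The strongest reply is that Section 8.2.1 already deals with worsening. It gives an abnormal laboratory finding as an example of an AE, calls earlier-onset laboratory abnormalities pre-existing, and makes exacerbation of a pre-existing condition a possible AE. A sensible investigator would put these together and report a worsening value. The exemption also applies to laboratory findings, so clinical worsening of, say, known kidney disease is an exacerbation in any case.

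This stands as far as it goes. A reader might infer that the protocol has no worsening language at all, or that out-of-range renal values are simply exempt. The documents support neither: the exemption follows only from the literal reading of one permissive bullet. What survives is that the bullet is the provision most specific to laboratory values, and a site that follows it is within the protocol.

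A reader might also infer that such changes would go unseen. They would not, given CTCAE toxicity assessment of every treated subject (Section 5.2), the change-from-baseline summaries and the laboratory data review. The bleeding rule in Section 13 counts bleeding that causes a hemoglobin fall of 2 g/dL or more, whatever the baseline. But a change-from-baseline summary carries neither grade nor attribution.

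On the late contacts, the reply is that the contacts also assess clinical status, and that protocol-defined AEs are collected for 28 days. If that term means every AE as Section 8.2.1 describes it, resolved events must be collected. The term is undefined, so it does not clearly close the gap. Even then, note f would not prompt the question that finds such events.

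**Conclusion.** The point holds as an unreconciled reporting rule of minor to moderate importance. The screening-abnormal bullet has no limit for worsening and no link to the exacerbation clause. On the literal reading, a value that worsens on drug can be missing from the graded and attributed AE counts. The late-contact gap is real but secondary: it concerns non-serious events that start and resolve between assessments, mostly after the drug has cleared.

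The size of any undercount cannot be determined. It depends on how many patients enter out of range, how many of those worsen, and how sites read the bullet, none of which the documents give. A reader might infer that the primary safety result is biased by a material, calculable amount. The documents do not support that: the endpoint is not defined as an AE count, no test or threshold uses the affected counts, and SAEs, deaths and the bleeding and mortality stopping rules have separate routes.

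**What to change.** (a) In Section 8.2.1, limit the screening-abnormal bullet to values that do not worsen from baseline by at least one CTCAE grade. Add a matching cross-reference between the onset-before-treatment bullet and the exacerbation clause. This brings the laboratory rules into line with the hospitalization exclusions.

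(b) In Table 4 note f, have each contact ask about all AEs since the last assessment, including those that have resolved. Define protocol-defined AE in Section 8.2.1 at the same time.

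(c) Optionally, add to Section 12.3 a table of baseline grade against worst on-treatment CTCAE grade, from the CBC and chemistry already collected daily.

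None of this needs a new visit, call or blood draw. The cost is a few wording edits, a somewhat higher reported AE count, some recall error for resolved events and slightly more tabulation.
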